7. SAFETY

The investigator or site staff is/are responsible during the study for the detection and documentation of events meeting the criteria and definition of an SAE as provided in this protocol.

Each subject will be instructed to contact the investigator immediately should they/the subject manifest any signs or symptoms they perceive as serious.

7.1. Safety definitions

7.1.1. Definition of an adverse event (Amended 19 October 2018)

An AE is any untoward medical occurrence in a subject, temporally associated with the use of a medicinal product, whether or not considered related to the medicinal product, or temporally associated with a study procedure.

Examples of an AE include

- Signs, symptoms, or the clinical sequelae of a suspected interaction.

Examples of an AE DO NOT include:

- Medical or surgical procedures (e.g., endoscopy, appendectomy); the condition that leads to the procedure is an AE.
- Situations where an untoward medical occurrence did not occur (e.g., social and/or convenience admission to a hospital, admission for routine examination).
- Anticipated day-to-day fluctuations of pre-existing disease(s) or condition(s) present or detected at the start of the study that do not worsen.
- ***Occurrence of a severe AECOPD, unless in the opinion of the Investigator this is related to study procedure.***

7.1.2. Definition of a serious adverse event

An SAE is any untoward medical occurrence that:

- a. Results in death,
- b. Is life-threatening,

Note: The term 'life-threatening' in the definition of 'serious' refers to an event in which the subject was at risk of death at the time of the event. It does not refer to an event, which hypothetically might have caused death, had it been more severe.

- c. Requires hospitalisation or prolongation of an existing hospitalisation,

Note: In general, hospitalisation signifies that the subject has been admitted at the hospital or emergency ward for observation and/or treatment that would not have been appropriate in the physician's office or in an out-patient setting.

Complications that occur during hospitalisation are also considered AEs. If a complication prolongs hospitalisation or fulfils any other serious criteria, the event will also be considered serious. When in doubt as to whether 'hospitalisation' occurred or was necessary, the AE should be considered serious.

Hospitalisation for elective treatment of a pre-existing condition (known or diagnosed prior to informed consent signature) that did not worsen from baseline is NOT considered an SAE.

- d. Results in disability/incapacity,

Note: The term disability means a substantial disruption of a person's ability to conduct normal life functions. This definition is not intended to include experiences of relatively minor medical significance such as uncomplicated headache, nausea, vomiting, diarrhoea, influenza like illness, and accidental trauma (e.g., sprained ankle) which may interfere or prevent everyday life functions but do not constitute a substantial disruption.

or

- e. Is a congenital anomaly/birth defect in the offspring of a study subject

Medical or scientific judgement should be exercised in deciding whether reporting is appropriate in other situations, such as important medical events that may not be immediately life-threatening or result in death or hospitalisation but may jeopardise the subject or may require medical or surgical intervention to prevent one of the other outcomes listed in the above definition. These should also be considered serious. Examples of such events are invasive or malignant cancers, intensive treatment in an emergency room or at home for allergic bronchospasm, blood dyscrasias or convulsions that do not result in hospitalisation.

7.1.3. Clinical laboratory parameters and other abnormal assessments qualifying as AEs or SAEs

In absence of diagnosis, abnormal laboratory findings (e.g., clinical chemistry, haematology, urinalysis) or other abnormal assessments that are judged by the investigator to be clinically significant will be recorded as AEs or SAEs if they meet the definition of an AE or an SAE (refer to Sections 7.1.1 and 7.1.2). Clinically significant abnormal laboratory findings or other abnormal assessments that are present at baseline and significantly worsen following the start of the study will also be reported as AEs or SAEs. However, clinically significant abnormal laboratory findings or other abnormal assessments that are associated with the disease being studied, unless judged by the investigator as more severe than expected for the subject's condition, or that are present or detected at the start of the study and do not worsen, will not be reported as AEs or SAEs.

The investigator will exercise his or her medical and scientific judgement in deciding whether an abnormal laboratory finding or other abnormal assessment is clinically significant.

7.2. Detecting and recording AEs, SAEs

7.2.1. Time periods for detecting and recording AEs and SAEs

AEs and SAEs related to study participation will be collected and recorded from the time of the first study visit until the subject is discharged from the study.

In order to fulfil international reporting obligations, SAEs that are related to study participation (i.e., protocol-mandated procedures, invasive tests, a change from existing therapy) will be collected and recorded from the time the subject consents to participate in the study/study start until she/he is discharged from the study.

AEs leading to withdrawal from the study, will be collected and recorded from the time of the first study visit until the subject is discharged from the study.

An overview of the protocol-required reporting periods for SAEs and AEs leading to withdrawal is given in [Table 10](#).

Table 10 Reporting period for SAE and AEs leading to withdrawal (Amended 19 October 2018)

Study activity	Screening Visit	Visit 1	Visit 2	Visit 3	AECOPD Visit	Study Conclusion
	Pre-Month 0	M 0	M 6	M 12	Within 96 hours of onset symptoms	
AEs/SAEs related to study participation*						
AEs/SAEs leading to withdrawal from the study						

**Study participation: Specific procedures required by study participation.*

7.2.2. Evaluation of SAEs (Amended 19 October 2018)

7.2.2.1. Active questioning to detect SAEs

Each subject/ will be instructed to contact the investigator immediately should the subject manifest any signs and symptoms (s)he perceives/ they perceive as serious. ***However, an occurrence of severe AECOPD is not defined as an SAE and therefore does not need to be reported as such, unless in the opinion of the Investigator this is related to a study procedure.***

All SAEs either observed by the investigator or his/ her staff or reported by the subject spontaneously or in response to a direct question will be evaluated by the investigator. The nature of each event, date and time of onset, outcome, intensity and possible relationship to the study procedures should be established.

When an AE/SAE occurs, it is the responsibility of the investigator to review all documentation (e.g., hospital progress notes, laboratory and diagnostics reports) relative to the event. The investigator will then record all relevant information regarding the AE/SAE in the eCRF. The investigator is not allowed to send photocopies of the subject's medical records to GSK Biologicals instead of appropriately completing the eCRF. However, there may be instances when copies of medical records for certain cases are requested by GSK Biologicals. In this instance, all subject identifiers will be blinded on the copies of the medical records prior to submission to GSK Biologicals.

The investigator will attempt to establish a diagnosis pertaining to the event based on signs, symptoms, and/ or other clinical information. In such cases, the diagnosis should be documented as the AE/SAE and not the individual signs/symptoms.

7.2.2.2. Assessment of causality

The investigator should assess the causality of each SAE. The investigator will use clinical judgement to determine the relationship between the SAEs and study participation. Alternative causes, such as natural history of the underlying diseases, other concomitant therapy and other risk factors will be considered and investigated.

There may be situations when a SAE has occurred and the investigator has minimal information to include in the initial report to GSK Biologicals. However, it is very important that the investigator always makes an assessment of causality for every event prior to submission of the SAE report to GSK Biologicals. The investigator may change his/her opinion of causality in light of follow-up information and update the SAE information accordingly.

If an event meets the criteria to be considered as 'serious' (see section 7.1.2), additional examinations/tests will be performed by the investigator in order to determine ALL possibly contributing factors to each SAE.

Possibly contributing factors include:

- Medical history.
- Concomitant medication.
- Protocol required procedure.
- Other procedure not required by the protocol.

7.2.2.3. Assessment of outcomes

The investigator will assess the outcome of all AEs (including SAEs) recorded during the study as:

- Recovered/ resolved.
- Recovering/ resolving.
- Not recovered/ not resolved.
- Recovered with sequelae/ resolved with sequelae.
- Fatal (SAEs only).

7.3. Reporting of SAEs

7.3.1. Prompt reporting of SAEs related to study participation to GSK

SAEs that occur in the time period defined in Section 7.2.1 will be reported promptly to GSK within the timeframes described in Table 11 once the investigator determines that the event meets the protocol definition of an SAE.

Table 11 Timeframes for submitting SAEs related to study participation to GSK

Type of event	Initial reports		Follow-up of relevant information on a previous report	
	Timeframe	Documents	Timeframe	Documents
SAEs related to study participation	24 hours*	Electronic/ Expedited Adverse Event Report	24 hours*	Electronic/ Expedited Adverse Event Report

* Timeframe allowed after receipt or awareness of the information.

7.3.3. Completion and transmission of SAEs reports related to study participation to GSK

Once an investigator becomes aware that an SAE has occurred in a study subject, the investigator (or designee) must complete the information in the electronic Expedited Adverse Event Report **WITHIN 24 HOURS**. The report will always be completed as thoroughly as possible with all available details of the event. Even if the investigator does not have all information regarding an SAE, the report should still be completed within 24 hours. Once additional information is received, the report should be updated **WITHIN 24 HOURS**.

The investigator will always provide an assessment of causality at the time of the initial report.

7.3.3.1. Back-up system in case the electronic reporting system does not work

If the electronic reporting system does not work, the investigator (or designee) must complete, then date and sign a paper Expedited Adverse Event Report and fax it to the GSK Biologicals Clinical Safety and Pharmacovigilance department within 24 hours.

This back-up system should only be used if the electronic reporting system is not working and **NOT** if the system is slow. As soon as the electronic reporting system is working again, the investigator (or designee) must complete the electronic Expedited Adverse Event Report within 24 hours. The final valid information for regulatory reporting will be the information reported through the electronic reporting system.

7.3.4. Updating of SAE after freezing of the subject's eCRF

When SAE information is received after freezing of the subject's eCRF, new or updated information should be recorded on a paper Expedited Adverse Event Report, with all changes signed and dated by the investigator. The updated report should be faxed to the GSK Biologicals Clinical Safety and Pharmacovigilance department or to the Study Contact for Reporting SAEs (see the [Sponsor Information](#)) within the designated reporting time frames specified in [Table 11](#).

Note: For studies using INFORM, freezing of the subject's eCRF would mean removal of write access in the subject's eCRF.

7.3.5. Regulatory reporting requirements for SAEs

The investigator will promptly report all SAEs to GSK Biologicals in accordance with the procedures detailed in Section [7.3.1](#). GSK Biologicals has a legal responsibility to promptly notify, as appropriate, both the local regulatory authority and other regulatory agencies about the safety of a product under epidemiological investigation. Prompt notification of SAEs by the investigator to the Study Contact for Reporting SAEs is essential so that legal obligations and ethical responsibilities towards the safety of other subjects are met.

7.4. Treatment of AEs

Treatment of any AE is at the sole discretion of the investigator and according to current good medical practice. Any medication administered for the treatment of a SAE (that are required to be reported as per protocol should be recorded in the Expedited Adverse Event Report of the subject's eCRF.

8. SUBJECT COMPLETION AND WITHDRAWAL

8.1. Subject completion

A subject who returns for the concluding visit foreseen in the protocol is considered to have completed the study.

8.2. Subject withdrawal

Subjects who are withdrawn because of AEs or SAEs related to study participation must be clearly distinguished from subjects who are withdrawn for other reasons.

From an analysis perspective, a 'withdrawal' from the study refers to any subject who did not come back for the concluding contact foreseen in the protocol.

All data collected until the date of withdrawal/last contact of the subject will be used for the analysis.

A subject is considered a 'withdrawal' from the study when no study procedure has occurred, no follow-up has been performed and no further information has been collected for this subject from the date of withdrawal/last contact.

Investigators will make an attempt to contact those subjects who do not return for scheduled visits or follow-up. The mode of contact will be by telephone. Three phone contacts will be made with an interval of one week between each phone call.

Information relative to the withdrawal will be documented in the eCRF. The investigator will document whether the decision to withdraw a subject from the study was made by the subject himself/herself or by the investigator, as well as which of the following possible reasons was responsible for withdrawal:

- SAE.
- Non-serious AE.
- Protocol violation (specify).
- Consent withdrawal, not due to an AE*.
- Moved from the study area.
- Lost to follow-up.
- Other (specify).

*In case a subject is withdrawn from the study because he/she has withdrawn consent, the investigator will document the reason for withdrawal of consent, if specified by the subject in the eCRF.

9. STATISTICAL METHODS

9.1. Endpoints

9.1.1. Primary endpoint (Amended 19 October 2018)

- Occurrence of potential bacterial and viral pathogens in sputum of stable COPD patients and during AECOPD, over the course of 1 year:
 - Bacterial pathogens, as identified by bacteriological methods, including (but not necessarily limited to) *H. influenzae*, *M. catarrhalis*, *S. pneumoniae*, *S. aureus*, *P. aeruginosa*, *K. pneumoniae* and *A. baumannii*.
 - Viral pathogens, as identified by PCR, including (but not necessarily limited to) RSV, parainfluenza virus, enterovirus/ HRV, metapneumovirus, influenza virus, adenovirus, bocavirus and coronavirus.

9.1.2. Secondary endpoints

- Occurrence of potential bacterial pathogens in sputum of stable COPD patients and during AECOPD, as measured by real-time qualitative PCR/ quantitative PCR and compared to data from bacteriological methods, over the course of 1 year:
 - Including (but not necessarily limited to) *H. influenzae*, *M. catarrhalis*, *S. pneumoniae*, *S. aureus* and *P. aeruginosa*.
- Occurrence of potential bacterial and viral pathogens (overall and by species) in sputum of stable COPD patients by GOLD grade, over the course of 1 year.
- Occurrence of potential bacterial and viral pathogens (overall and by species) in sputum during AECOPD by severity of AECOPD, over the course of 1 year.
- Incident rate (per subject per year) of AECOPD, overall and by GOLD grade, over the course of 1 year.
- Severity of AECOPD, overall and by GOLD grade, over the course of 1 year.
- Duration of AECOPD, overall and by AECOPD severity, over the course of 1 year.
- CAT score in stable COPD patients and during AECOPD, over the course of 1 year.
- SGRQ-C score in stable COPD patients, over the course of 1 year.
- FEV₁% of predicted normal value in stable COPD patients, at Pre-Month 0 and Month 12.
- Healthcare utilisation, over the course of 1 year.

9.1.3. Tertiary endpoints

- EXACT-PRO scores in stable COPD patients and during AECOPD, over the course of 1 year.
- Bacterial load measured by both culture and PCR in COPD and during AECOPD.
- HRV load measured by PCR in COPD and during AECOPD.

9.2. Determination of sample size

The primary objective of this study is to describe the proportion of bacterial and viral pathogens (overall and by species) detected in sputum in stable COPD and during AECOPD.

Assuming around 90% of the All Enrolled Set participated in the study, on average 1 AECOPD visit and 80% of the above population set can provide an evaluable sputum sample at AECOPD, for 240, 200, 160, and 50 enrolled subjects, one may expect around 180, 140, 120, 40 sputum samples, respectively. Assuming that results from these sputum samples are independent and that the between country variability is much smaller than the within country variability, we would have the following 95% exact confidence interval for different incidences in sputum samples from exacerbations (see [Table 12](#)).

Table 12 Exact 95% confidence intervals of the percentage of occurrence of a specific bacterium from sputum collected during AECOPD

%	Number of evaluable sputum samples during AECOPD			
	N=180	N=140	N=120	N=40
5	[2.3 ; 9.3]	[2.0 ; 10.0]	[1.9 ; 10.6]	[0.6 ; 16.9]
10	[6.0 ; 15.3]	[5.6 ; 16.2]	[5.3 ; 16.8]	[2.8 ; 23.7]
20	[14.4 ; 26.6]	[13.7 ; 27.6]	[13.3 ; 28.3]	[9.1 ; 35.6]
30	[23.4 ; 37.3]	[22.6 ; 38.3]	[22.0 ; 39.0]	[16.6 ; 46.5]
40	[32.8 ; 47.6]	[31.8 ; 48.6]	[31.2 ; 49.3]	[24.9 ; 56.7]
50	[42.5 ; 57.5]	[41.4 ; 58.6]	[40.7 ; 59.3]	[33.8 ; 66.2]

N = total number of evaluable sputum samples during AECOPD.

One of the secondary objectives is to estimate the incidence rate of all-cause AECOPDs in the study population.

Assuming around 80% of the all enrolled set completed the study, for 240, 200, 160 and 50 subjects enrolled, one would have at least 190, 160, 130 and 40 subjects evaluable respectively. Assuming further that around 80% of the subjects can provide an evaluable sputum sample at AECOPD, this would lead to around 150, 130, 100, 30 subjects (see [Table 13](#)).

Table 13 95% confidence intervals of AECOPD incidence rates with different overdispersion values

			$\Phi = 1$		$\Phi = 1.5$		$\Phi = 2$	
0.2 AECOPD/ subject/ year			95% CI*		95% CI*		95% CI*	
T	n	Value (n/T)	LL	UL	LL	UL	LL	UL
30	6	0.20	0.04	0.36	0.00	0.40	-0.03	0.43
100	20	0.20	0.11	0.29	0.09	0.31	0.08	0.32
130	26	0.20	0.12	0.28	0.11	0.29	0.09	0.31
150	30	0.20	0.13	0.27	0.11	0.29	0.10	0.30
1 AECOPD/ subject/ year			95% CI*		95% CI*		95% CI*	
T	n	Value (n/T)	LL	UL	LL	UL	LL	UL
40	40	1.00	0.69	1.31	0.62	1.38	0.56	1.44
130	130	1.00	0.83	1.17	0.79	1.21	0.76	1.24
160	160	1.00	0.85	1.15	0.81	1.19	0.78	1.22
190	190	1.00	0.86	1.14	0.83	1.17	0.80	1.20
2 AECOPD/ subject/ year			95% CI*		95% CI*		95% CI*	
T	n	Value (n/T)	LL	UL	LL	UL	LL	UL
40	80	2.00	1.56	2.44	1.46	2.54	1.38	2.62
130	260	2.00	1.76	2.24	1.70	2.30	1.66	2.34
160	320	2.00	1.78	2.22	1.73	2.27	1.69	2.31
190	380	2.00	1.80	2.20	1.75	2.25	1.72	2.28
3 AECOPD/ subject/ year			95% CI*		95% CI*		95% CI*	
T	n	Value (n/T)	LL	UL	LL	UL	LL	UL
40	120	3.00	2.46	3.54	2.34	3.66	2.24	3.76
130	390	3.00	2.70	3.30	2.64	3.36	2.58	3.42
160	480	3.00	2.73	3.27	2.67	3.33	2.62	3.38
190	570	3.00	2.75	3.25	2.70	3.30	2.65	3.35

* Normal approximation with variance = $\Phi n/T^2$, where Φ is the overdispersion factor for a Poisson distribution (calculations performed in Microsoft Excel).

T = Total number of evaluable subjects; n = Total number of exacerbations; CI = confidence interval; LL = lower limit; UL = upper limit.

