9.6. Analysis of secondary objectives

The proportion of sputum samples obtained at each visit (confirmed stable visits* and AECOPD visits [any severity, mild, moderate and severe]) and positive for specific bacterial pathogens by both bacteriological methods and PCR (overall and by bacterial species) will be computed with 95% confidence intervals.

** A confirmed stable visit will be defined as a scheduled study visit for which the investigator confirms in the eCRF that the subject is stable / has recovered from a previous exacerbation.*

The proportion of sputum samples obtained at each stable visit and positive for specific bacterial/viral pathogens by bacteriological methods and PCR, respectively (overall and by bacterial/ viral species) will be computed with 95% confidence intervals, by GOLD grade at enrolment.

The proportion of sputum samples obtained at each AECOPD visits and positive for specific bacterial/ viral pathogens by bacteriological methods and PCR, respectively (overall and by bacterial/viral species) will be computed with 95% confidence intervals, by AECOPD severity.

The proportion of sputum samples obtained at each confirmed stable/AECOPD visit with previous administration of antibiotics or not and positive for specific bacterial/ viral pathogens by bacteriological culture and PCR, respectively (overall and by bacterial/viral species) will be computed with 95% confidence intervals.

The following incidence rates will be computed, with 95% confidence intervals (CI):

- All-cause AECOPD.
- AECOPD having sputum containing bacterial pathogens found by PCR *or* by bacteriological methods or by both methods (overall and by, but not limited to, the following bacterial species: *H. influenzae*, *M. catarrhalis*, *S. pneumoniae*, *S. aureus*, and *P. aeruginosa*).

The 95% CI of the incidence rate will be computed using a model which accounts for repeated events. The Generalised linear model assuming the Negative Binomial distribution for the response variable with logarithm as link function, and the logarithm of time for follow-up as an offset variable will be used. The incidence rates described above will also be computed for mild, moderate severe AECOPD and by GOLD grade at enrolment and will be estimated by country.

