11.5. Methodology for computing CI

- All CI computed will be two-sided at 95% significant level.
- The exact 95% CIs for a proportion within a group will be calculated using Clopper Pearson method [[Clopper 1934](#)].

12. ANNEX 2: AECOPD DEFINITION AND CALCULATION RULE**12.1. Definition, onset, recovery, duration of an AECOPD event**

AECOPD events are confirmed according to investigator judgment after an AECOPD visit which is aimed to exclude worsening in symptoms not related to an AECOPD event.

AECOPD visits are scheduled after an electronic Diary Card alert confirmed by the investigator (by phone call or at the study site) or after spontaneous site visits due to worsening symptoms without any alert.

Electronic Diary Card alerts refer to daily symptoms recorded the morning after (also called morning symptoms). Alerts are based on the Anthonisen criteria:

- Worsening of two or more of the following major symptoms for at least two consecutive days*^{***}: dyspnea, sputum volume, sputum purulence (colour)

Or

- Worsening of any major symptom together with any of the following minor symptoms for at least two consecutive days*^{***}: sore throat, colds (nasal discharge and/or nasal congestion), fever (oral temperature $\geq 37.5^{\circ}\text{C}$) without other cause, increased cough, increased wheeze.

** The same two symptoms do not have to be present on both days as long as at least one major symptom is present on both days.*

CONFIDENTIAL

201112 (EPI-NTHI-001 BOD APA)
 Statistical Analysis Plan Amendment 2 Final

AECOPD onset will be defined as the first day of the two consecutive days of worsening symptoms.

AECOPD recovery will be determined/confirmed by the investigator/delegate during (a) follow-up phone call(s) which will take place every 2 weeks until the AECOPD has resolved. The end date will be based on when the investigator/delegate determines that the AECOPD symptoms have resolved. In determining this end date, consideration will be given to symptoms recorded in the electronic Diary Card and patient assessment during the phone calls.

AECOPD duration will be defined as the number of days from AECOPD onset (included) and AECOPD recovery (not included).

Duration = date2 – date1 + 1,

with date2: AECOPD recovery date,

date1: AECOPD onset date

12.2. Recovery and duration of an exacerbation according to EXACT-PRO:

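### Table 13 states AECOPD rate precision on a different scale from the planned negative binomial analysis, so it prints one impossible limit (-0.03) and sets both limits too low in the 0.2/year block

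*Protocol*

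**What the plan says.** Protocol 9.2 gives Table 13 as the precision expected for the incidence rate of all-cause AECOPD, a secondary objective. With 80% of enrolled subjects completing, 240, 200, 160 and 50 enrolled become evaluable counts as follows: "one would have at least 190, 160, 130 and 40 subjects evaluable respectively". A further 80% providing evaluable AECOPD sputum gives about 150, 130, 100 and 30. As a set, these smaller counts head only the 0.2/year block.

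The footnote defines the method as a normal approximation to the rate n/T with variance Φn/T², where Φ "is the overdispersion factor for a Poisson distribution (calculations performed in Microsoft Excel"). Three values of Φ are shown: 1, 1.5 and 2. Two rows of the 0.2/year block matter here. The columns are T, n, rate, then lower and upper limits for each Φ:

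- 50 enrolled: "30 6 0.20 0.04 0.36 0.00 0.40 -0.03 0.43"
- 200 enrolled: "130 26 0.20 0.12 0.28 0.11 0.29 0.09 0.31"

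For the analysis itself, Protocol 9.6 specifies "The Generalised linear model assuming the Negative Binomial distribution for the response variable with logarithm as link function", with log follow-up time as an offset. SAP 6.3.4.4 repeats this model, and its code takes Wald limits for the log rate and exponentiates them. SAP 11.5 sets the level: "All CI computed will be two-sided at 95% significant level".

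**The concern.** A table of expected precision should show what the planned analysis will deliver. An interval built on the log scale is asymmetric and always above zero. An interval built on the rate scale is symmetric and can fall below zero when events are few, which is how the table comes to print -0.03. Neither document comments on that value or explains the change of scale. Table 12, in the same section, uses exact intervals that stay within bounds.

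The issue is confined to sparse data. The 0.2/year block uses the reduced, sputum-evaluable counts, so it reads as the precision for pathogen-associated or otherwise infrequent AECOPD rates. A reader relying on it would expect a lower upper limit than the model will report. Table 13 is also the only precision statement in the plan for incidence.

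**Working it through.** **Inputs.** T, n, Φ and the printed limits come from Table 13; z = 1.96 from the two-sided 95% level; the log link and exponentiated Wald limits from Protocol 9.6 and SAP 6.3.4.4. Assumption: one year of follow-up per evaluable subject.

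**Step 1: reproduce the table.** The footnote's formula is n/T ± 1.96 × √(Φn)/T. For T=30, n=6, Φ=2: 0.20 ± 1.96 × √12/30 = 0.20 ± 0.2263, giving -0.0263 to 0.4263, printed as -0.03 to 0.43. All 96 printed limits reproduce to two decimals.

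**Step 2: the scale of the planned model.** For an intercept-only log-link negative binomial with mean μ and dispersion k, the variance of the log rate is (1/μ + k)/T. Writing Φ = 1 + kμ and n = μT, this equals Φ/n. The interval is therefore (n/T) × exp(±1.96√(Φ/n)). For the same cell: √(2/6) = 0.5774; 1.96 × 0.5774 = 1.1316; 0.20 × exp(±1.1316) = 0.065 to 0.620.

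**Step 3: the 0.2/year block.**

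| T (enrolled) | Φ | Printed | Log scale |
|---|---|---|---|
| 30 (50) | 1 | 0.04 to 0.36 | 0.090 to 0.445 |
| 30 (50) | 1.5 | 0.00 to 0.40 | 0.075 to 0.533 |
| 30 (50) | 2 | -0.03 to 0.43 | 0.065 to 0.620 |
| 130 (200) | 1 | 0.12 to 0.28 | 0.136 to 0.294 |
| 130 (200) | 1.5 | 0.11 to 0.29 | 0.125 to 0.320 |
| 130 (200) | 2 | 0.09 to 0.31 | 0.116 to 0.344 |

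Log-scale upper limits exceed the printed ones by 24%, 33% and 44% at T=30, and by 5%, 10% and 11% at T=130. Both limits rise in every row, so much of the change is a shift. Compared without rounding, the width at T=130 goes from 0.154 to 0.158 (Φ=1) and from 0.217 to 0.228 (Φ=2), which is about 3% and 5%. At T=30 it goes from 0.320 to 0.355 (Φ=1, 11%) and from 0.453 to 0.556 (Φ=2, 23%).

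**Step 4: is this an artefact of the log-Wald formula?** At Φ=1 the exact Poisson limits are 0.073 to 0.435 at T=30 and 0.131 to 0.293 at T=130. Both sit above the printed intervals, in the same direction as the log-scale ones.

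**Step 5: higher rates.** At 1/year, T=160 (200 enrolled in that block), the printed intervals are 0.85-1.15, 0.81-1.19 and 0.78-1.22; the log-scale ones are 0.856-1.168, 0.827-1.209 and 0.803-1.245. Across all rows with a rate of 1 or more and T of 130 or more, upper limits differ by at most 2.8%. In the T=40 rows the difference is 1.3% to 7.6%.

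**Step 6: coverage of the printed method, with Φ known.** At 0.2/year and T=30 it is 93.5%, 88.9% and 85.0% for Φ=1, 1.5 and 2. At Φ=2, 14.5% of intervals lie wholly below the true rate. At T=130 coverage is 94.9% (Φ=1) and 93.0% (Φ=2). At 1/year and T=160 it is about 94.5-95%.

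**The case against.** The strongest reply is that nothing depends on the table. Incidence is a secondary objective, SAP 7 calls all analyses descriptive, no target width is set, and the reported intervals will come from the SAP model. The approximation is disclosed in the footnote. The largest gaps sit in the row for 50 enrolled, while the target is about 200; at that size, coverage of the printed method is close to nominal and width barely changes. The stated objective is all-cause AECOPD, for which 9.2 plans on an average of one AECOPD visit, and at 1/year the two methods nearly agree. All of this stands, and it limits the point to a correction of stated figures.

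Three stronger readings might be inferred, and the documents do not support them.

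- *That Table 13 contains an arithmetic error.* It does not; every limit follows from the footnote. The fault is the choice of scale.
- *That the planned sample is too small or its precision seriously overstated.* At T=130 the interval mainly shifts upward, and the 85% coverage belongs only to T=30 with Φ=2.
- *That Φ should rise with the rate, as 1 + k × rate, making the 3/year intervals too narrow.* The algebra is right for a negative binomial with constant k, but the documents give no value of k. Φ=2 at 0.2/year corresponds to k=5, whereas Φ=2 at 3/year corresponds to k=0.33, so the result depends wholly on an assumed k. SAP 6.3.4.4 even provides a Poisson fallback in case the data are underdispersed. The three Φ values are best read as a labelled set of scenarios.

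**Conclusion.** The point holds as a minor one. Table 13 follows its own footnote but not the planned analysis. It prints one limit that a rate cannot take, and in the 0.2/year block both limits are too low. The gap in the upper limit is large only at T=30 (0.36/0.40/0.43 printed against 0.45/0.53/0.62). At the target enrolment it is modest (0.28/0.29/0.31 against 0.29/0.32/0.34), and for rates of 1/year or more with T of at least 130 it is negligible.

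This rests on one year of follow-up per evaluable subject, an intercept-only model, and Φ treated as known. Estimating the dispersion would add some uncertainty in the small rows.

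**What to change.** Recompute every row of Table 13 as (n/T) × exp(±1.96√(Φ/n)) at the Φ values already stated (1, 1.5, 2), replace the printed limits, and amend the footnote to say that they are log-scale limits matching Protocol 9.6 and SAP 6.3.4.4. Keep the Φ columns as scenarios. The cost is one recalculated table and slightly less favourable upper limits, mostly in the 0.2/year block. The enrolment target, the analysis model and the SAP code need no change.
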